## **Statistical Considerations**

## Data Management

The Data Management Group, part of the Coordinating Center, has primary responsibility for randomization and analyzing data generated by the clinical centers. Data will be collected on hard-copy forms at each site and transformed to an electronic database. Our web-based management system will assure integrity and validity. Dynamic reports and periodic statistical analyses will monitor quality. A participant-based inventory system will track recruitment, retention, adherence, and missing data from entry through exit, close-out, and lock-down of final datasets. Our team developed a similar database for the IDEA and START studies.

## Statistical Analyses

Statistical analyses will be conducted according to intention-to-treat principles using SAS.

# Primary Aim.

The primary hypothesis of long-term reduced WOMAC pain at 18 months will be tested based on a two-tailed significance level of 0.05 using contrast statements from a repeated measures mixed linear model with time (6, 18 mos), randomization arm (D+E vs control), and the interaction, which adjusts the means at each time point for potential missing data bias (Laird and Ware). Intervention-effect estimates will be further adjusted for baseline pain values, BMI, county, and gender; analysis will match design, so the variance estimate will not be biased. Participant ID number will be included as a random effect to control for within-subject variability, and the longitudinal model will use an unstructured covariance matrix. In the unlikely event the model does not converge, a first-order autoregressive (AR[1]) covariance structure will be fit instead. Maximum-likelihood techniques will estimate parameters, as in the IDEA trial (Messier et al). Preliminary analyses will be conducted to check the shape of the distributions and variances between groups and as a function of the covariates. Regression diagnostics and residual plots will help to find appropriate transformations, if necessary. We will include exploratory analyses of subgroups, defined by gender, age (<70 vs  $\geq$ 70 years), baseline BMI (27.0-34.9, 35-44.9,  $\geq$ 45 kg/m^2), county, and race to determine any differential pain responses.

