## Nutrition & Health Intervention

The nutrition and health (attention control) intervention will cover an 18-month period. There will be five total face to face group meetings over the 18 months, with one meeting each at months 1, 3, 6, 9, and 15; and during the other months (months 2, 4-5, 7-8, 10-14, 16-18) participants will receive a combination of informational packets, webinars, text messages, and emails. Participants will be able to select their preferred method. Each group meeting will last approximately one hour and will be held at St. Peter's World Outreach Center and at Senior Services in Winston-Salem, NC. The sessions will be interactive and will provide useful information on such topics as proper foot care, general nutrition, health behaviors, management of medications, and sleep practices. The Community Advisory Board will give input on the class sessions.

Experts across a broad range of relevant topics that are of interest to older adults will provide information via information packets, webinars, text messages or emails. These monthly contacts and email blasts will keep the participants in the nutrition and health group engaged in the WE-CAN study and will increase adherence to the group sessions and the testing visits.

Participants in both interventions will be provided with items with the study logo such as t-shirts and tote bags to promote group bonding and study adherence. Additionally, giftcards will be raffled at various class sessions. In order to better balance the amount of money spent on the two groups participants in the Nutrition & Health group will receive a \$100 (gift cards) for completing the testing appointments. They will be given \$25 at 6 months and \$75 at 18 months. At the 12-month testing appointments the participants will receive an incentive with the study logo. Participants in the Diet & Exercise group will be receiving meal replacements for the first year of the study.

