### Procedures-Screening and Follow-up Visits.

Measurements	PSV	SV1	FU6	FU12	FU18	Explanation
	1	1	Ċ	Questionna	ires	-
Informed Consent		х				
Eligibility Questionnaire	х					To determine eligibility
Medical History/Med History FU	хс	х	х	x	x	For eligibility and to document changes in health
Risk Stratification	хс	х				Used to screen cardiovascular risk
Comorbidities Questionnaire		х		х	х	
Randomization		х				
WOMAC		х	x	x	x	Pain is primary and function secondary outcomes. Will be taken from the KOOS
Knee Injury and Osteoarthritis Outcome Score (KOOS)		x	х	x	х	Assesses patient's opinion about their knee and associated problems
PASE scale		х	х	х	х	Physical Activity Scale for the Elderly
MOCA		х			х	Montreal Cognitive Assessment
EuroQol Quality of Life(EQ5D)		х	х	х	Х	Quality of life measure
Resource Utilization		x	х	x	x	Visits to clinicians, tests, medications, injections, surgery, alternative therapies
Work Productivity and Activity Impairment Index		х	х	x	x	assesses absenteeism and presenteeism
DHQ II		х	х	х	х	NIH Diet History Questionnaire
SF-36		х	х	х	х	Health related quality of life (physical, mental)
Health Literacy		х	Х	х	х	
Adherence Self Efficacy		x	х	x	x	Confidence in exercising at various intensities and frequencies
Adherence for Duration		Х	Х	х	х	Confidence in walking for different durations
Gait Efficacy		Х	Х	х	х	Confidence in completing tasks
Demographics		Х				
Medication form		х	х	х	х	Atherosclerosis Risk in Communities form
Weight Efficacy Questionnaire		х	х	х	х	Self-Efficacy for Weight Management
PANAS		х	х	x	х	Positive and Negative Affect Scale
SWL		х	х	x	х	Satisfaction with Life
Perceived Stress		х	х	х	х	Stress
Pain Catastrophizing Scale		х	х	Х	х	Catastrophizing
Intermittent and Constant Osteoarthritis Pain (ICOAP)		x	х	x	Х	Intermittent and Constant Pain
CES-D		х	х	x	Х	Depression
Transition Questionnaire			х	х	Х	Knee pain
Adverse Events			х	Х	Х	Also collected as they occur
	-		sical Perf	ormance T	ests/Knee E	
height	XC	х				To determine BMI
weight	XC	х	х	х	Х	To determine BMI
Knee exam		х				To determine eligibility
6 minute walk		х	х		X	Measure of mobility
Expanded Short Physical		х	х	х	Х	Gait speed, sit to stand, balance tests; predicts
Performance Battery (SPPB)						disability
GaitRite		X	X	X	X	mobility measures
Stair Climb xc = brief screen by self-report, P		Х	х	х	Х	mobility measure

Procedures-Screening and Follow-up Visits.

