12-month Follow-up Data Collection Visit (FU12): Participants will return to Worrell Professional Building to repeat all measures collected at baseline (minus the knee exam and demographics). The testing session will last approximately 2.5 - 3.5 hours.

18-month Follow-up Data Collection Visit (FU18): Participants will return to Worrell Professional Building to repeat all measures collected at baseline (minus the knee exam and demographics). The testing session will last approximately 2.5 - 3.5 hours. At the end of 18 months the participants will have a mini session on what the other group received.

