# Missing Data

If missing data are related to outcomes, our results could be biased. Our models will include variables from previous visits determined to predict loss to satisfy Little and Rubin's conditions for data considered missing at random (MAR). If "informative censoring" occurs, we will compare analyses using subjects with complete data, multiple imputations, or explicit modeling of the censoring mechanism (Conaway, 1993, Wu and Bailey, 1989).

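### The primary mixed model uses WOMAC pain at 6 and 18 months but not the scheduled 12-month score, so its missing-data adjustment ignores the latest pain value of anyone lost after month 12

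*Combined protocol and SAP*

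**What the plan says.** Primary Aim: the 18-month hypothesis is tested by a contrast from a "repeated measures mixed linear model with time (6, 18 mos), randomization arm (D+E vs control), and the interaction". Estimation is by maximum likelihood with an unstructured covariance, adjusted for baseline pain, BMI, county and gender. The section says of this model: "which adjusts the means at each time point for potential missing data bias".

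Procedures-Screening and Follow-up Visits: the WOMAC row of the schedule is marked at SV1, FU6, FU12 and FU18, with the note "Pain is primary and function secondary outcomes. Will be taken from the KOOS". The FU12 paragraph says: "Participants will return to Worrell Professional Building to repeat all measures collected at baseline (minus the knee exam and demographics"). WOMAC is therefore collected at 12 months, and it is also kept in the reduced set for remote or mailed collection.

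Missing Data: "Our models will include variables from previous visits determined to predict loss", with the aim of meeting the missing-at-random condition. If informative censoring occurs, "we will compare analyses using subjects with complete data, multiple imputations, or explicit modeling of the censoring mechanism". No visit or variable is named.

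Nutrition & Health Intervention: "In order to better balance the amount of money spent on the two groups participants in the Nutrition & Health group will receive a" total of 100 dollars in gift cards for testing visits, 25 at 6 months and 75 at 18 months. The diet and exercise (D+E) arm's meal replacements are described for the first year.

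**The concern.** A likelihood-based repeated-measures model corrects for dropout only through the outcomes it contains. For someone seen at months 6 and 12 but not at 18, the specified model predicts 18-month pain from baseline and 6-month pain. The 12-month score, which is closest to the loss and probably the best predictor, is not used.

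This matters when two things hold together: late loss depends on 12-month pain beyond what baseline and 6-month pain explain, and either that dependence or the amount of loss differs by arm. The plan's own incentives make unequal late loss possible, since only the control arm is paid for testing visits (mostly at month 18) and D+E meal replacements are described for the first year only. The documents do not show that loss will differ. At stake is the single primary contrast, with 20% loss planned for.

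**Working it through.** **Inputs from the document (Primary Outcomes, Aim 1).** 410 per arm, 80% retention (328 per arm), SD 3.50, baseline-to-18-month correlation 0.4, means 5.03 and 5.92, difference 0.887, two-sided 0.05.

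**The plan's own figure.** Conditional SD = 3.50 × √(1 − 0.4²) = 3.21. Standard error = 3.21 × √(2/328) = 0.251. Power = Φ(0.887/0.251 − 1.96) = 94%, as stated. It uses baseline and 18-month values only, so the choice of visits does not change it.

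**Assumptions not in the document.** Follow-up correlations 0.60 (6–12 months), 0.65 (12–18) and 0.50 (6–18). Loss before month 12 is completely random. Late loss is a share of those still in the trial at month 12, with log-odds of loss changing by 0.5 or 1.0 per SD of 12-month pain. For example, 12.6% early and 8.5% late loss give 0.874 × 0.915 = 80% retained.

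**Method.** Large-sample simulation, 1.5 million per arm, compared with the full-data baseline-adjusted estimate (Monte Carlo error 0.003 or less). With loss that is not recovered, the two likelihood estimates of the 18-month effect are:

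- 6/18 model: b(arm) + b(6) × effect at 6 months, where the b's come from regressing 18-month pain on arm, baseline and 6-month pain.
- 6/12/18 model: d(arm) + d(6) × effect at 6 months + d(12) × effect at 12 months, with 12-month pain added to that regression.

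**Bias in points (D+E minus control; minus means the benefit is overstated), for log-odds 0.5 and 1.0.**

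| Late loss | 6/18 model | 6/12/18 model |
|---|---|---|
| Depends on 12-month pain in D+E only, 2.5% | −0.014, −0.027 | −0.001, −0.001 |
| Same, 5% | −0.026, −0.051 | 0.000, 0.000 |
| Same, 8.5% | −0.046, −0.086 | −0.001, −0.001 |
| Same slope in both arms, control 6% / D+E 11% | −0.029, −0.050 | −0.002, −0.002 |
| Same slope, 4% / 13% | −0.050, −0.088 | −0.002, −0.001 |
| Same slope, 2.7% / 14.2% (85% vs 75% retained) | −0.063, −0.113 | −0.002, −0.002 |
| Opposite slopes by arm, 8.5% (extreme) | −0.091, −0.174 | 0.000, 0.000 |
| Same slope and same loss (log-odds 1.0 only) | −0.003 to −0.001 | −0.002 to 0.000 |

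The sign reverses if the dependence or the imbalance reverses. Rounding scores and limiting them to 0–20 hardly changes the 8.5% D+E-only row (−0.042, −0.083). Separate simulations with other loss and correlation assumptions gave 0.03 to 0.29 points, the upper end needing 20% late loss and opposite slopes.

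**Effect on the test.** Error rate = P(|Z + bias/0.251| > 1.96). A bias of 0.05 gives 5.5%, 0.09 gives 6.5% and 0.17 gives 10.4%. In the other direction, 0.09 toward the null gives Φ((0.887 − 0.09)/0.251 − 1.96) = 89% power.

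**Limits of the repair (8.5%, D+E only).**

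- Loss driven by 18-month pain itself: −0.103, −0.193 falls only to −0.080, −0.150, about a fifth.
- Loss driven equally by 12- and 18-month pain: −0.081, −0.154 falls to −0.044, −0.084, about half.
- If 10%, 20% or 30% also miss month 12 at random, up to −0.008, −0.017 or −0.025 remains.

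**If 12-month pain were entered as an ordinary covariate.** Let r be the 12-to-18-month correlation. With equal effects at both visits and a 0.4 correlation of each with baseline, the effect shrinks by 0.887 × (r − 0.16)/0.84. That is 0.41, 0.52 and 0.62 points for r = 0.55, 0.65 and 0.75.

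**The case against.** The strongest reply is that the Missing Data section already covers this. In every scenario where the 6/18 model is biased by 12-month pain, that score predicts loss, so it is just the kind of variable the section promises to include. With about 358 per arm reaching month 12 and a logistic check at p < 0.05 (an assumed rule; the plan gives none), a pooled check would flag it in 94–100% of trials under a common slope with unequal loss. Under D+E-only dependence at 8.5% loss it would flag it in 45–93%, or 74–99.7% if checked within that arm. Where detection is poorest among the D+E-only cases (19% at 2.5% loss), the bias is only 0.014.

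This stands in part, and it narrows the point. It does not close it. A pooled check would catch opposite slopes only 11% of the time. More importantly, flagging a variable does not say how it enters. The covariate reading is admittedly the less natural one: month 12 is not a previous visit for the 6-month outcome, and people without the score would drop out. But the text does not exclude it. Multiple imputation is named only as a conditional comparison, not as the primary test.

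It is also fair that the plausible biases are under half a standard error, that loss patterns are assumed, that the gift cards are presented as balancing spending, and that remote WOMAC collection should reduce loss. These points limit the size of the problem. The 6/18 structure may have been deliberate, since the 6-minute walk row is unmarked at FU12, but no rationale is stated.

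**Conclusion.** The concern holds. The primary model omits a scheduled measurement of the primary outcome while claiming to adjust for missing data, and the Missing Data section fills the gap only conditionally and without saying how. The likely bias is modest: about 0.01 to 0.11 points on an effect of 0.887, reaching 0.17 under opposite slopes, and about zero when loss is the same in both arms. These sizes rest on assumed late loss, log-odds and follow-up correlations. Adding month 12 brings the bias to within 0.003 points when loss after month 12 is explained by observed pain and the 12-month score is available. This is a change that should be made, not a flaw that undermines the trial, and confidence in its practical size is moderate.

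**What to change.** In Primary Aim, list time as 6, 12 and 18 months for WOMAC pain, with month 12 as a repeated outcome and the 18-month contrast still primary. Do the same under Secondary Aims for WOMAC function and the SF-36 physical score, which are also marked at FU12. If the sponsor prefers 6 and 18 months, the plan should say why.

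In Missing Data, state that follow-up values of an outcome enter only as repeated outcomes or as imputation variables, never as covariates. Keep the multiple-imputation and censoring-model comparisons, because month 12 gives only partial protection against loss that depends on unseen 18-month pain.

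The cost is wording only. The 12-month data are already scheduled, remote WOMAC collection is already provided for, and sample size and stated power do not change.

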# Secondary Aims

Repeated measures mixed linear models similar to Aim 1 will be used to analyze WOMAC function, 6-minute walk, and SF-36 physical subscale. Each outcome will be modeled separately, and 18-month effectiveness will be tested based on a two-tailed significance level of 0.05. The model will include the fixed effects study arm, time, time-group interaction, county, gender, baseline BMI, and baseline values of the outcome; participant ID number will be included as a random effect, and an unstructured covariance will be used assuming model convergence is not a problem (AR[1] otherwise). Preliminary analyses will be conducted to check the shape of the distributions and variances between groups and as a function of the covariates. Regression diagnostics and residual plots will help to find appropriate transformations, if necessary.

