## **Primary Outcomes**

Aim 1. A total sample of 820 (410/group) will provide 94% statistical power to detect differences  $\geq 15\%$  in pain at the 2-sided 0.05 significance level with 80% retention (2-sample t-test, Nquery Advisor). Based on ADAPT (Messier et al). The D+E group in IDEA reduced pain by an average of 51%. This approach utilizes the conditional variance approach of Borm et al. for the estimation of power for ANCOVA models using group standard deviation  $\sigma = 3.50$ , Pearson correlation between baseline and 18-month pain score of  $\rho = 0.4$  for a conditional standard deviation  $\sigma_c = 3.21$  ( $\sigma_c = \sqrt{1 - \rho^2} \times \sigma$ ), and 18-month treatment WOMAC pain means ~D+E

Table 2: Detectable absolute a         410/group, 80% retention, 85%         18M values is p .	modifications in retention and treatment effect are				
Variable	Anticipated 18m Control mean*	Standard Deviation	ρ	D+E Mean (% change from C)	presented in Table 1. Correlation
WOMAC Function	17.5	11.5	0.6	15.3 (-12.3%)	between baseline
Mobility: 6-Minute Walk (m)	509	90.7	0.7	524 (3.0%)	and 18 month pain
SF-36 Physical Score (0-100)	42.0	10.1	0.5	44.1 (4.9%)	values are

= 5.03 vs E-only control = 5.92 ( $\Delta$  = -0.887). Variations of anticipated power due to

WOMAC Function17.511.50.615.3 (-12.3%)between baselineMobility: 6-Minute Walk (m)50990.70.7524 (3.0%)and 18 month painSF-36 Physical Score (0-100)42.010.10.544.1 (4.9%)values areestimated from the IDEA trial, while anticipated treatment effects and standard deviation for painwere obtained using weighted averages of D+E and non-D+E treatments from the ADAPT andIDEA studies, with some attenuation of the anticipated treatment effect due to the pragmatic

nature of WE-CAN (Table 1).

 Table 1: Power estimates for WOMAC pain, assuming baseline N=820, correlation between BL and 18 months=0.4, and common group SD = 3.50.

18 month Control Mean WOMAC	18 Month D+E WOMAC Pain (% difference from	18-Month Retention						
Pain	Control)	70%	75%	80%	85%			
		Power						
	5.15 (13%)	81%	84%	86%	88%			
5.00	5.03 (15%)	91%	92%	94%	95%			
5.92	4.91 (17%)	96%	97%	97%	98%			

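### As listed, the mixed model gives baseline pain one slope for months 6 and 18; a baseline-by-time term would protect the 18-month contrast if loss depends on baseline pain differently by arm

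*Combined protocol and SAP*

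**What the plan says.** Under Statistical Analyses, the Primary Aim section specifies a repeated measures mixed model with time (6 and 18 months), arm and their interaction. It adds that "Intervention-effect estimates will be further adjusted for baseline pain values, BMI, county, and gender". The covariance is unstructured and estimation is by maximum likelihood. The plan relies on this model for missing data, describing it as one "which adjusts the means at each time point for potential missing data bias".

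The Secondary Aims section sets out the parallel model for WOMAC function, 6-minute walk and the SF-36 physical score in full: "The model will include the fixed effects study arm, time, time-group interaction, county, gender, baseline BMI, and baseline values of the outcome". Time by group is the only interaction in that list.

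The Missing Data section adds variables that predict loss, to support the missing-at-random (MAR) assumption. It says nothing about how the baseline outcome enters the model.

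The Primary Outcomes section (sample size) computes power from an ANCOVA conditional variance, using a "Pearson correlation between baseline and 18-month pain score of" 0.4. That calculation concerns month 18 alone.

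**The concern.** Programmed as listed, the model estimates a single coefficient for the baseline outcome and applies it at both visits. If baseline pain predicts month 6 more strongly than month 18, that coefficient is a compromise, too steep for month 18. Likelihood estimation protects against MAR loss only when the mean model is right, and a shared slope is a restriction this trial does not need.

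The restriction does no harm if the arms stay balanced on baseline pain among those still observed. It matters if loss shifts baseline pain differently in the two arms, because the wrong slope then mis-corrects the imbalance. That is conceivable here. The plan allows for 20% loss, and the arms differ widely in burden: three exercise sessions a week plus diet sessions, against five face-to-face meetings in 18 months. At stake is a shift in the primary 18-month contrast that adding predictors of loss would not cure, since baseline pain is already in the model. The secondary models share the same structure.

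**Working it through.** **Inputs from the documents.** Two-sided 0.05 ("based on a two-tailed significance level of 0.05"). "A total sample of 820 (410/group) will provide 94% statistical power" and "at the 2-sided 0.05 significance level with 80% retention", so 0.80 × 410 = 328 per arm. Means "5.03 vs E-only control = 5.92", with a stated difference of 0.887. SD 3.50 and baseline-to-18-month correlation 0.4.

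**The plan's own figure.**
- Conditional SD = 3.50 × √(1 − 0.4²) = 3.208.
- SE = 3.208 × √(2/328) = 0.251.
- Power = Φ(0.887/0.2505 − 1.960) = Φ(1.58) = 94.3% (noncentral t: 94.2%).

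The stated 94% reproduces.

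**Effect of a shared slope on the SD alone.** If slope b is used at month 18 in place of 0.4, the residual SD is √(3.208² + (b − 0.4)² × 3.5²).
- b = 0.5: SD 3.227, power 94.1%.
- b = 0.6: SD 3.283, power 93.3%.

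The fitted shared slope lies between the two visits' slopes, so the loss is smaller in practice. The model SD at month 18 is 3.21 for a 6-month slope of 0.5 and 3.24 for 0.6. The latter gives Φ(0.887/(3.24 × √(2/328)) − 1.960) = Φ(1.55) = 93.9%. This costs one point or less.

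**Effect on the contrast.** Assumed, because the documents do not give them: SD 3.5 at every visit (so slope equals correlation), 6-to-18-month correlation 0.6, loss reaching 20% at month 18, and loss logistic in baseline pain alone (hence MAR). The two-visit model was fitted by maximum likelihood with unstructured covariance to very large simulated samples (of the order of 1.5 million participants per scenario), once with a shared slope and once with visit-specific slopes. The true difference is −0.887. Entries are shared-slope bias in points; where two estimates are shown, the entry is the shared-slope estimate minus the visit-specific one on the same data.

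| Log-odds of loss per SD of baseline pain | 6-month slope 0.4 | 0.5 | 0.6 |
|---|---|---|---|
| Equal in both arms | 0 | 0 | 0 |
| +0.25 in one arm, 0 in the other | 0 | 0.013 | 0.028 |
| +0.5 in D+E, −0.5 in control | 0 | 0.047 (−0.850 vs −0.897) | 0.103 (−0.786 vs −0.889) |
| +1 in D+E, 0 in control | 0 | no more than 0.05 | 0.094 (−0.783 vs −0.877) |

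The mechanism can be checked by hand. At a 6-month slope of 0.6 the shared slope is about 0.53. Under +0.5/−0.5, completers' baseline means differ by about 0.67 points. The mis-correction is roughly (0.53 − 0.40) × 0.67 = 0.09, close to the fitted 0.10.

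**What a bias of 0.10 would do (SE 0.251, 0.10/0.251 = 0.398).**
- Type I error: Φ(−1.960 + 0.398) + Φ(−1.960 − 0.398) = 0.059 + 0.009 = 6.8%.
- Power if the effect is attenuated: Φ(0.787/0.251 − 1.960) = Φ(1.18) = 88%.
- Power if the direction is reversed: Φ(0.987/0.251 − 1.960) = Φ(1.97) = 97.6%.

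A bias of 0.03 gives type I error 5.2% and power 92.7%.

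**After the change.** With visit-specific slopes the contrast was unbiased to within simulation error in every scenario. In simulated trials of 820, power was 94-95% and type I error about 4.4-5.8%.

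**The case against.** The strongest reply is that everything that creates the bias is assumed. The documents give the baseline-to-18-month correlation only. That baseline predicts a nearer visit better is a general expectation, not something the plan shows. What matters is the slope, which is the correlation times the SD ratio. With a month-6 SD 20% lower, a correlation of 0.5 gives a slope of 0.5 × 0.8 = 0.4 and no bias; a correlation of 0.6 with log-odds +1 in one arm gives 0.045 rather than about 0.10. Log-odds of 0.5 to 1.0 per SD are odds ratios of 1.6 to 2.7, which is strong dependence. At +0.25 in one arm the bias is 0.013 to 0.028, or 1.5% to 3% of 0.887. All of this stands, and it is why the sizes are a range rather than an estimate for this trial.

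It can also be said that the plan never states in words that the slope is shared, and that it promises regression diagnostics and residual plots. The first point is fair: this is a natural reading of an incomplete specification, not a declared choice. But the Secondary Aims list names its interaction explicitly and includes no other, and nothing in the diagnostics commits the analyst to freeing the slope.

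A reader might go further and infer that the conditional SD of 3.21 fails, so that the 94% power is wrong. The documents do not support that: the figure reproduces, and SD inflation alone costs a point or less. Nor does loss that depends on baseline pain differently by arm suffice by itself; with equal slopes at the two visits there is no bias.

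**Conclusion.** The point holds as a specification gap with a conditional consequence. Read naturally, the model constrains the baseline slope to be equal at months 6 and 18. Bias in the 18-month contrast needs both unequal true slopes and loss that depends on baseline pain differently by arm; if either is absent, it is zero. Under the stated assumptions it is about 0.01-0.05 points at a 6-month slope of 0.5 and 0.03-0.10 at 0.6, at most about 12% of the planned difference (0.103/0.887). It is smaller if the month-6 SD is lower, and its sign depends on which arm loses more participants with high baseline pain. Nothing in the documents shows that it will occur, and the sample size calculation is unaffected. The case for change is that the protection is almost free and aligns the analysis with the month-18 ANCOVA on which power was computed.

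**What to change.** In the Primary Aim section, state that baseline pain enters the model together with its interaction with time. In the Secondary Aims section, add the interaction of the baseline outcome value with time to the listed fixed effects. The month-18 contrast then uses the month-18 baseline slope. It remains a single number, because baseline is not interacted with arm.

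Interactions of BMI, county and gender with time are optional, since no bias was shown for them.

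The cost is a sentence in each section, one extra term in each model, and one degree of freedom per model against about 656 expected completers (2 × 328). No new data are needed and the sample size does not change. Settling this before the arms are compared also removes a modelling choice that would otherwise be made after seeing the primary result.
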